5. To assess the safety profiles in the simultaneous and sequential group participants by baseline COVID-19 serostatus	5a. To compare secondary outcomes 3a, 3b, 3c, and 4a according to baseline COVID-19 serostatus
6. To assess the safety profiles in the simultaneous and sequential group participants by vaccine product (Pfizer or Moderna).	6a. To compare secondary outcomes 3a, 3b, 3c, and 4a according to vaccine product (Pfizer or Moderna).
7. To assess the effect of simultaneous administration of IIV4 and COVID-19 vaccine on IIV4 immunogenicity as assessed by hemagglutination inhibition assay (HAI)	
7a. The proportion of participants in each vaccination group with a seroprotective HAI titer ($\geq 1:40$) pre- and post-IIV4 immunization for each IIV4 antigen
 
7b. The proportion of participants in each vaccination group achieving seroconversion following IIV4 (an HAI titer $\geq 1:40$ following IIV4 if the baseline titer is $< 1:10$ or a four-fold rise in HAI titer if the baseline titer is $\geq 1:10$) for each IIV4 antigen
 
7c. The geometric mean HAI titer (GMT) for each IIV4 antigen pre- and post-IIV4 in each vaccination group
 
7d. The geometric mean fold rise (GMFR) in HAI titer for each vaccination group

8. To assess serum antibody levels to SARS-CoV-2 antigens	8a. The proportion of participants in each vaccination group seropositive to SARS-CoV-2 variants tested prior to and following mRNA COVID-19 vaccine

	8b. The geometric mean ID ₅₀ and ID ₈₀ titers of neutralizing antibodies for each SARS-CoV-2 variant tested pre- and post-mRNA COVID-19 vaccine in each vaccination group
--	---

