6.2 Influenza Hemagglutination Inhibition (HAI) Assay

Influenza Hemagglutination Inhibition (HAI) Assays will be performed on sera collected, contingent on additional funding. Briefly, reference wild-type, reassortant, or vaccine virus strains representative of the specific viral antigens included in the 2021-22 influenza vaccine will be used to evaluate the relative levels of all four influenza strain-specific antibodies in

participant serum samples collected pre- and 21 or 28 days post-vaccination from all study participants. To accomplish these activities, all participant samples will be interrogated for influenza antibodies against the strains of interest using the influenza hemagglutination inhibition assay (HI). This assay is considered the “gold-standard” measure by which to evaluate seroconversion/seroprotection in response to seasonal influenza vaccination. This assay will be performed in accordance with the Duke Regional Biocontainment Laboratory Virology Unit’s fully optimized and approved SOP (RVUSOP004 Influenza HI of Serum Samples). Briefly, test samples will be assayed by HAI as duplicate 2-fold dilution series starting at 1:10. Serum dilutions are then incubated with a concentration of virus verified to possess a known potential for red blood cell (RBC) agglutination. The presence of virus-specific antibodies is visualized via incubation of the virus-serum mixture with a RBC solution; the endpoint titer for a given dilution series is then expressed as the reciprocal of the final dilution in which complete HAI is observed. By convention, seronegative samples are defined as having an endpoint HAI titer < 40 and seropositive samples as having an endpoint titer of $\geq 1:40$; and seroconversion as a 4-fold change in endpoint titer relative to pre-immunization baseline or a change from <10 to $\geq 1:40$ ⁵¹.

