The proportion of participants in each vaccination group with a seroprotective HAI titer ( $\geq 1:40$ ) pre- and post-IIV4 immunization for each IIV4 antigen will be compared using a Mantel-Haenszel statistic in a stratified analysis by site to control for the randomization blocks at the two-sided alpha 0.05 level.

The proportion of participants in each vaccination group achieving seroconversion following IIV4 (an HAI titer  $> 1:40$  following IIV4 if the baseline titer is  $< 1:10$  or a four-fold rise in HAI titer if the baseline titer is  $> 1:10$ ) for each IIV4 antigen will be compared using a Mantel-Haenszel statistic in a stratified analysis by site to control for the randomization blocks at the two-sided alpha 0.05 level.

The geometric mean HAI titer (GMT) for each IIV4 antigen pre- and post-IIV4 in each vaccination group will be compared (within vaccine group pre versus post and between vaccination groups) using a regression model with the log transformed titer value at the two-sided alpha 0.05 level. The geometric mean fold rise (GMFR) in HAI titer for each vaccination group will be presented along with a 95% confidence interval.

The Immunogenicity Population is the primary analysis population.

8. EO8: Assessments of the serum antibody levels to SARS-CoV-2 antigens.

The proportion of participants in each vaccination group seropositive to SARS-CoV-2 variants tested prior to and following mRNA COVID-19 vaccine will be compared using a Mantel-Haenszel statistic in a stratified analysis by site to control for the randomization blocks at the two-sided alpha 0.05 level. Comparisons will be made pre- and post-vaccination for each variant tested. The definition of seropositive is as follows:

- $ID_{50}$  above Limit of Detection (LOD) at baseline
- after vaccination and seronegative at baseline,  $ID_{50}$  above LOD is considered seropositive
- after vaccination and seropositive at baseline, then an  $ID_{50}$  3-fold over baseline  $ID_{50}$  is considered seropositive.

The term  $ID_{50}$  refers to the inhibitory dilution where 50% neutralization occurs, and  $ID_{80}$  refers to the inhibitory dilution where 80% neutralization occurs.  $ID_{50}$  estimates are generally used for analysis purposes since they are in the linear part of the curve and more stable estimates.

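### The SAP's EO8 seropositivity rule mixes seropositivity with seroresponse, and the strict signs in the HAI seroconversion rule leave attainable titres unclassified or failed

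*SAP*

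**What the plan says.** **EO8, SARS-CoV-2 neutralisation.** Protocol Section 2 (8a) describes the outcome as the proportion "seropositive to SARS-CoV-2 variants tested prior to and following mRNA COVID-19 vaccine". SAP 8.3 defines seropositive in three parts:

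- At baseline: ID50 above the limit of detection (LOD).
- "after vaccination and seronegative at baseline": ID50 above LOD.
- "after vaccination and seropositive at baseline, then an" ID50 "3-fold over baseline" ID50 is required.

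The proportions are compared with a site-stratified Mantel-Haenszel statistic at two-sided 0.05, and "Comparisons will be made pre- and post-vaccination for each variant tested".

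**EO7, influenza HAI.** SAP 3.3 (EOM7b) and SAP 8.3 define seroconversion as a titre >1:40 if baseline is <1:10, "or a four-fold rise in HAI titer if the baseline titer is" >1:10. The Protocol Summary has the same strict signs. Protocol Section 2 (7b) has ≥1:40 and ≥1:10. Protocol 6.2 describes "seroconversion as a 4-fold change in endpoint titer relative to pre-immunization baseline or a change from <10 to" ≥1:40. The same section fixes the grid: "test samples will be assayed by HAI as duplicate 2-fold dilution series starting at 1:10".

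**The concern.** In EO8 one label covers two quantities. For a participant already above LOD, the post-vaccination question is no longer whether antibody is detectable but whether it has tripled. Someone whose titre doubles from a high baseline is tabulated as seropositive before vaccination and not seropositive after it. Protocol 1.2 expects most adults and many children in the trial to be receiving a booster, so this branch of the rule may well apply to most of the sample. A reader of the results table would take the post figure for a seropositivity rate.

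In EO7 the issue is a boundary on a discrete scale. Exact titres of 1:10 and 1:40 are ordinary results of a 2-fold series starting at 1:10, so the choice between > and ≥ changes who is classified and how. A programmer working from the SAP would have to invent a rule for baseline 1:10, and the result would not match the definition in Protocol Section 2.

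**Working it through.** The plan states no figure that depends on these rules, so there is nothing to reproduce. The check enumerates what each rule does.

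**EO8, individual level.** Baseline ID50 above LOD, post value 2.9 times baseline: positive before, not positive after, although both values exceed LOD. This needs no assumption.

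**EO8, group level.** Let q be the share positive at baseline, r the share of those reaching a 3-fold rise, and s the share of baseline negatives ending above LOD. The SAP's post-vaccination share is

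q·r + (1 − q)·s.

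The documents give none of these quantities. Assume s = 1, q from 0.5 to 1.0 and r from 0.3 to 0.9:

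| q (pre share) | r = 0.3 | r = 0.5 | r = 0.7 | r = 0.9 |
|---|---|---|---|---|
| 50% | 65% | 75% | 85% | 95% |
| 80% | 44% | 60% | 76% | 92% |
| 95% | 33.5% | 52.5% | 71.5% | 90.5% |
| 100% | 30% | 50% | 70% | 90% |

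With s = 1 the share falls when q·r + (1 − q) < q, that is, when r < 2 − 1/q. At q = 0.8 this is r < 0.75. At q = 0.5 it is r < 0, so no fall is possible. Judged against LOD throughout, every post share in the table would be 100%, provided no one drops below LOD.

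To link r to the size of the response, assume that log10 fold rise is normal with SD 0.4:

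r = 1 − Φ((log10 3 − log10 GMFR)/0.4).

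- GMFR 2: 1 − Φ(0.440) = 33%
- GMFR 4: 1 − Φ(−0.312) = 62%
- GMFR 8: 1 − Φ(−1.065) = 86%

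With q = 1 these are the post-vaccination shares, against 100% before.

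**EO7, grid.** Take baseline <10, 10, 20, 40, 80 and post-vaccination <10, 10, 20, 40, 80, 160, 320, which gives 5 × 7 = 35 cells.

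| Cells | Strict signs | Protocol Section 2 signs |
|---|---|---|
| <10 to 40 (1 cell) | not seroconverted | seroconverted |
| 10 to 40, 80, 160 or 320 (4 cells) | no rule | seroconverted |
| 10 to <10, 10 or 20 (3 cells) | no rule | not seroconverted |
| other 27 cells | same | same |

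So 8 of 35 cells differ, and 5 of those 8 are seroconversions under ≥. These are counts of cells, not of participants.

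To show how often a titre of exactly 1:40 might arise among participants with baseline <1:10, assume that the log2 titre before rounding down to the grid is normal, with μ = log2(median/10):

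P(titre = 1:40) = Φ((3 − μ)/SD) − Φ((2 − μ)/SD).

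With a median of 40 or 80, this is 25% for SD 1.5 and 19% for SD 2. With median 80 and SD 1.5, P(≥1:40) = 75% and P(>1:40) = 50%. These figures apply only to the baseline <1:10 subgroup, whose size the documents do not give.

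**The case against.** **The Mantel-Haenszel test compares arms, not time points.** The SAP asks explicitly for within-group pre/post comparison of titres, but not of these proportions, so the sentence on pre- and post-vaccination comparisons may mean arms compared at each time. A baseline-conditional response compared between randomised arms is valid. This stands. A reader might infer that the rule biases the arm comparison, but nothing in the documents shows that. What remains is that the reported outcome is the proportion seropositive before and after vaccine, and the post figure is not one.

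**An LOD-only endpoint may be uninformative.** If nearly everyone is positive at baseline, it sits near 100% in both arms, and the 3-fold rule avoids that ceiling. This also stands. It supports keeping the 3-fold criterion under its own name.

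**The SAP alone departs from the protocol on HAI.** A reader might infer this, but it is not so. The Protocol Summary carries the same strict signs, so the protocol disagrees with itself. Nor does Protocol 6.2 contain ≥1:10; it states a 4-fold change or a move from <10 to ≥1:40. That wording does cover both boundary titres, but SAP 8.3 restates its own definition and does not point to 6.2.

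**The sign may have been lost in text conversion.** This is possible: one column header in Appendix B shows a damaged ≥. Against it, ≥1:40 for seroprotection reads correctly in the Protocol Summary, SAP 3.3 and SAP 8.3. The source PDF must settle it. If it shows ≥ throughout, the HAI part falls. The EO8 part does not depend on any sign.

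**Conclusion.** The EO8 rule is wrong as labelled. Its post-vaccination proportion combines seropositivity with seroresponse and cannot be set beside the baseline proportion. That conclusion needs no assumed input. The size of any apparent fall does: the 33% to 86% range assumes that all are positive at baseline and that the SD is 0.4. A reader might infer that the proportion will fall, but the documents give no baseline rate. A fall is plausible with mainly booster enrolment, while at 50% positivity with s = 1 the share rises.

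The HAI definition is inconsistent between sections, subject to the PDF check. Under the strict signs, baseline 1:10 has no rule and <1:10 to 1:40 is a failure. A reader might infer that 1:40 is lost generally. It is lost only as a post titre from baseline <1:10; seroprotection keeps ≥1:40. No effect on overall seroconversion is quantified, because the share with baseline <1:10 is unknown.

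The consequences are confined to exploratory outcomes EO7 and EO8, and Protocol 6.2 makes the HAI assays conditional on further funding. The primary analysis, seroprotection, GMT and GMFR are unaffected. The wording should be corrected before these outcomes are analysed.

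**What to change.** **EO8.** In SAP 8.3, report seropositivity as ID50 above LOD at every time point. Report separately a named seroresponse: ID50 at least 3-fold over baseline if baseline positive, above LOD if baseline negative. Writing at least 3-fold also settles how an exact 3-fold rise is counted. Make seroresponse the between-arm response endpoint.

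**EO7.** Check the signs against the source PDF. Then, in SAP 3.3, SAP 8.3 and the Protocol Summary, define seroconversion as a titre ≥1:40 with baseline <1:10, or a rise of at least 4-fold with baseline ≥1:10, in line with Protocol Section 2.

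The cost is SAP wording, one correction to the Protocol Summary and one additional EO8 summary. No new assays, visits or participants are needed.

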3 STUDY DESIGN

3.1 Main study design

This study is a prospective, randomized, clinical trial to assess the safety of simultaneous versus sequential administration of mRNA COVID-19 and IIV4 vaccines in 450 persons age ≥ 5 years enrolled at Duke University Medical Center (Lead Contractor), Johns Hopkins University (Contributing Contractor), and Cincinnati Children's Hospital Medical Center (Contributing Contractor). Participants will be enrolled in the 2021-2022 and 2022-2023 influenza seasons. Individuals will be enrolled who have not received their influenza vaccine during the influenza season during which they are recruited and are either receiving a booster dose of mRNA COVID-19 vaccine (for ages booster is authorized and recommended) or are receiving a primary two-dose mRNA COVID-19 vaccine series (5 years of age or older). Future mRNA COVID vaccines may include SARS-CoV-2 viral variants which may be included in this study if authorized or approved by the FDA and recommended by the CDC. Health, demographic and health-related quality of life (HRQOL) data will be collected from study participants 12 years of age or older at baseline. All participants receiving an mRNA COVID-19 vaccine on Day 1 (Visit 1) will be randomized to receive quadrivalent inactivated influenza vaccine (IIV4) or placebo. Persons aged < 65 years will receive standard dose IIV4 (SD-IIV4) or saline placebo injection. To qualify for the study, children < 9 years of age must only need to receive a single dose of IIV4 per ACIP recommendations for the 2022-2023 season. Persons aged ≥ 65 years will receive high-dose IIV4 (HD-IIV4) or saline placebo injection. Participants will receive the vaccines in an observer-blinded manner on the same day as they receive mRNA COVID-19 vaccine. Seven to fourteen days later (Visit 2) those who received IIV4 at Visit 1 will receive placebo and those who received placebo on at Visit 1 will receive IIV4 (SD-IIV4 or HD-IIV4, depending upon age). Participants will then receive a second mRNA COVID-19 vaccine (Visit 3), if applicable, and according to the recommended schedule for vaccination for the respective mRNA COVID-19 vaccine product used.

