Vaccine lot numbers, dose, and site of vaccine administration will be recorded by research staff. After administration, used study syringes will be disposed of according to standard operating procedure.

Emergency management supplies including epinephrine (1:1000) and trained staff will be available for initial treatment of an allergic reaction, if needed.

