6.3 COVID-19 Immunogenicity

The Duke NAb Laboratory for HIV and SARS-CoV-2 Vaccine Research and Development (Duke NAb Lab, PI: [name]) will assess the magnitude, kinetics and duration of neutralizing antibody responses against SARS-CoV-2 by using a validated assay in an environment that operates in compliance with Good Clinical Laboratory Practices (GCLP).

Neutralization of SARS-CoV-2 Spike-pseudotyped viruses will be assessed in 293T/ACE2 cells as described in SOP “CFAR02-A0026 Measuring Neutralizing Antibodies Against SARS-CoV-2 Using Pseudotyped Virus and 293T/ACE2 Cells.” This assay has been formally validated and is part of Drug Master File # 26862 with the US Federal Drug Administration. Assay validation was performed with human serum samples and monoclonal antibodies using the D614G form of the Wuhan-1 Spike, which is the dominant form of Spike protein in the global epidemic. This assay has also been validated using B.1.351(246R) and B.1.1.529 (BA1) and may be validated for other newly emerged variants as needed.

Neutralization is measured by using lentiviral particles pseudotyped with SARS-CoV-2 Spike and containing a firefly luciferase (Luc) reporter gene for quantitative measurements of infection by relative luminescence units (RLU). SARS-CoV-2 Spike-pseudotyped viruses are prepared and titrated for infectivity by using mutated forms of an expression plasmid encoding codon-optimized full-length Spike of the Wuhan-1 strain (VRC7480) provided by Drs. [name] and [name] at the Vaccine Research Center, National Institutes of Health (USA). Mutations were introduced into VRC7480 by site-directed mutagenesis using the QuikChange Lightning Site-Directed Mutagenesis Kit from Agilent Technologies. All mutations were confirmed by full-length Spike gene sequencing. Pseudovirions are produced in HEK 293T/17 cells by transfection using Fugene 6 Transfection Reagent and a combination of Spike plasmid, lentiviral backbone plasmid (pCMV $\Delta R8.2$) and firefly Luc reporter gene plasmid (pHR' CMV Luc) in a 1:17:17 ratio in Opti-MEM (Life Technologies). Pseudovirions are titrated for infectious dose (TCID50) by making serial 3-fold or 5-fold dilutions in quadruplicate for a total of 11 dilutions in 96-well flat-bottom plates.

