f) EOM6a: To compare secondary outcomes 3a, 3b, 3c and 4a according to COVID-19 vaccine product (Pfizer or Moderna).

g) EOM7a. The proportion of participants in each vaccination group with a seroprotective HAI titer ( $\geq 1:40$ ) pre- and post-IIV4 immunization for each IIV4 antigen.

EOM7b: The proportion of participants in each vaccination group achieving seroconversion following IIV4 (an HAI titer  $> 1:40$  following IIV4 if the baseline titer is  $< 1:10$  or a four-fold rise in HAI titer if the baseline titer is  $> 1:10$ ) for each IIV4 antigen.

EOM7c: The geometric mean HAI titer (GMT) for each IIV4 antigen pre- and post-IIV4 in each vaccination group.

EOM7d: The geometric mean fold rise (GMFR) in HAI titer for each vaccination group.

h) EOM8a: The proportion of participants in each vaccination group seropositive to SARS-CoV-2 variants tested prior to and following mRNA COVID-19 vaccine.

EOM8b: The geometric mean ID50 and ID80 titers of neutralizing antibodies for each SARS-CoV-2 variant tested pre- and post-mRNA COVID-19 vaccine in each vaccination group.

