## 4 STUDY DESIGN

### 4.1 Study Description

This study is a prospective, randomized, clinical trial to assess the safety of simultaneous versus sequential administration of mRNA COVID-19 and IIV4 vaccines in 450 persons age  $\geq 5$  years enrolled at Duke University Medical Center (Lead Contractor), Johns Hopkins University (Contributing Contractor), and Cincinnati Children's Hospital Medical Center (Contributing Contractor). Participants will be enrolled in the 2021-2022 and 2022-2023 influenza seasons. Individuals will be enrolled who have not received their influenza vaccine during the influenza season during which they are recruited and are either receiving a booster dose of mRNA COVID-19 vaccine (12 years of age or older) or are receiving a primary two-dose mRNA COVID-19 vaccine series (5 years of age or older). Health, demographic and health-related quality of life (HRQOL) data will be collected from study participants at baseline for participants aged  $\geq 12$  years. All participants receiving an mRNA COVID-19 vaccine on Day 1 (Visit 1) will be randomized to receive quadrivalent inactivated influenza vaccine (IIV4) or placebo injection. Persons aged  $< 65$  years will receive standard dose IIV4 (SD-IIV4) or saline placebo injection. Children  $< 9$  years of age must only need to receive a single dose of IIV4 per ACIP recommendations for the 2022-2023 season. Persons aged  $\geq 65$  years will receive high-dose IIV4 (HD-IIV4) or saline placebo injection. Participants will receive the vaccines in an observer-blinded manner on the same day as they receive mRNA COVID-19 vaccine. Seven to fourteen days later (Visit 2) those who received IIV4 at Visit 1 will receive placebo and those who received placebo on at Visit 1 will receive IIV4 (SD-IIV4 or HD-IIV4, depending upon age). Participants will then receive a second mRNA COVID-19 vaccine (Visit 3), if applicable, and according to the recommended schedule for vaccination for the respective mRNA COVID-19 vaccine product used.

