#### 4.2.2.2 Quantitative SARS-CoV-2 assessments

Participants will have blood draws on Day 1 (before vaccination) and following each vaccination according to schedules outlined in Section 5.1 to be stored for serum COVID-19 neutralization assays. COVID-19 neutralizing antibody titers will be compared between groups receiving COVID-19 and IIV4 simultaneously or sequentially for each variant tested.

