The geometric mean  $ID_{50}$  and  $ID_{80}$  titers pre- and post-vaccination with mRNA COVID-19 will be compared (within vaccine group pre versus post and between vaccination groups) using a regression model adjusting for vaccine platform (Pfizer or Moderna) and study site with the log transformed titer geometric mean  $ID_{50}/ID_{80}$  values at the two-sided alpha 0.05 level. Should there exist a substantial difference (based on a statistical evaluation of these data) in titer values between the vaccine platforms, these proposed analysis and tables will be done within vaccine platform type (i.e., separate analyses for Pfizer or Moderna). This decision will be made with the study team once all data have been collected and are ready for analysis. Tables will be generated to present the geometric mean raw  $ID_{50}$  and  $ID_{80}$  values pre- and post-vaccination by vaccination group.

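### The EO8 neutralising-titre model has no term for COVID-19 vaccine formulation; if more than one formulation is used, the arm comparison loses some precision but stays unbiased

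*SAP*

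**What the plan says.** SAP 8.3, EO8, compares geometric mean ID50 and ID80 titres within and between vaccination groups on the log scale, using a "regression model adjusting for vaccine platform (Pfizer or Moderna) and study site". Its one contingency is to repeat the analysis separately for Pfizer and Moderna if the platforms differ substantially. That decision is left until all data are in.

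Protocol 3.1 allows the COVID-19 vaccine composition to change during the trial: "Future mRNA COVID vaccines may include SARS-CoV-2 viral variants which may be included in this study if authorized or approved by the FDA", with a CDC recommendation also required. SAP 4.1 gives the enrolment period: "Participants will be enrolled in the 2021-2022 and 2022-2023 influenza seasons".

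The endpoint is variant-specific. SAP 4.2.2.2 states that "COVID-19 neutralizing antibody titers will be compared between groups receiving COVID-19 and IIV4 simultaneously or sequentially for each variant tested". Protocol 6.3 adds that the assay "may be validated for other newly emerged variants as needed".

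No other text supplies a formulation term:
- Protocol 5.2.1 stratifies randomisation by age group, primary series or booster, and site.
- SAP 7.1 lists vaccine product received and influenza season as baseline descriptors only.
- Protocol 7.1.8 defers the exploratory analyses to the SAP.

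On data capture, Protocol 5.3.1 states: "Vaccine lot numbers, dose, and site of vaccine administration will be recorded by research staff".

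**The concern.** The SAP already accepts that the vaccine received may affect titres, because it adjusts for manufacturer and would split the analysis if manufacturers differ. Antigen composition is at least as direct a candidate for influencing a titre against a particular variant. Yet the platform term pools original-strain and variant-containing products of the same brand, and the planned split by manufacturer would still mix them.

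What is at stake is precision. For a variant contained in one formulation and not in another, any difference in titre between recipients of the two would count as residual variation. The interval for the Simultaneous-to-Sequential ratio would then be wider than it needs to be, for the variants that a change of formulation is meant to address.

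**Working it through.** **Plan's own figure.** The documents state no sample size, power or SD for EO8. The only stated power is for the primary noninferiority test. With 15% in both groups, margin 0.10, 214 per group and one-sided alpha 0.025, it is Φ(0.10/√(2×0.15×0.85/214) − 1.96) = Φ(2.897 − 1.960) = 0.826. This reproduces the stated 82.6%. It concerns a different endpoint and does not change here.

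**Inputs for EO8.** The covariates (platform and site) are from SAP 8.3, and 1:1 allocation is from Protocol 5.2.1. Three inputs are assumptions, because the documents give none of them:
- SD within formulation (s): 0.5 to 0.6 log10
- share on the variant-containing product (f): 0.3 to 0.5
- fold difference in titre between formulations (k): 2, 3 or 4

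**Formulas.** Variance between formulations: V = (log10 k)² × f(1−f). Share of variance explained: R² = V/(s² + V). Narrowing of the interval on the log scale when the term is added: 1 − √(1 − R²).

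| Fold k | (log10 k)² | R², low corner (s 0.6, f 0.3) | R², high corner (s 0.5, f 0.5) | Interval narrower by |
|---|---|---|---|---|
| 2 | 0.0906 | 0.0190/0.3790 = 5.0% | 0.0227/0.2727 = 8.3% | 2.5% to 4.2% |
| 3 | 0.2276 | 0.0478/0.4078 = 11.7% | 0.0569/0.3069 = 18.5% | 6.0% to 9.7% |
| 4 | 0.3625 | 0.0761/0.4361 = 17.5% | 0.0906/0.3406 = 26.6% | 9.1% to 14.3% |

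These gains are upper bounds for each set of inputs. R² here is formulation's marginal share, and the model already contains platform and site. If the formulation mix differs by brand or site, those terms already absorb part of it.

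**Wider grid.** With s from 0.4 to 0.6, f from 0.2 to 0.5 and k from about 1.4 to 4, omitting the term widens the interval by 0.5% to 25%.

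**Bias and error rate.** A simulation of 4,000 trials used 428 participants, s 0.5, f 0.5 and a 3-fold difference, with formulation independent of platform and site. It fitted the model with and without the formulation term:
- Mean arm estimate with no true effect: −0.0003 in both models.
- Type I error: 5.3% without the term, 5.0% with it.
- Standard error: 0.054 without, 0.049 with.
- Power for an arm difference of 0.135 log10 (ratio 1.37): 70.5% without, 78.4% with.

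The figure of 428 is the planned evaluable total for the primary endpoint. The documents give no expected size for the Immunogenicity Population.

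**The case against.** The strongest reply is that the documents establish neither the premise nor the occasion. Protocol 3.1 says only that variant-containing vaccines may be included, and no passage reports titres by formulation. A reader might infer that two formulations were used, or that formulation is an established driver of variant-specific titres. The documents support neither inference. The point is therefore conditional and its size rests on assumptions.

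A reader might also infer that, because formulation is not a stratification factor, a chance imbalance would pass for an effect of co-administration. That does not stand as a separate harm. Chance imbalance is already reflected in the standard error, and the simulation shows no bias and a type I error near 5%. Permuted blocks within strata would also tend to balance a product change that follows calendar time. For scale, a 3-point imbalance in formulation share with a 3-fold difference moves the log10 ratio by 0.03 × 0.477 = 0.014, or about 3% on the ratio.

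It is also fair to say that the EO8 text names no term for baseline titre, age group or primary series versus booster, and the last two are randomisation strata. Formulation is thus one candidate among several. This argues for reviewing the covariate list as a whole; it does not justify leaving formulation out.

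Finally, capture of formulation is not shown for every dose. Staff record lot numbers, but Protocol 5.1 and 5.3.1 allow the COVID-19 vaccine to be given as standard of care, up to 8 hours before enrolment at Visit 1. The documents do not expressly say that formulation is recorded for those doses. That objection stands and affects the cost of the fix.

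**Conclusion.** The point holds as a minor, conditional one. The EO8 model omits formulation although the protocol admits more than one formulation and the endpoint is variant-specific. If more than one is used in the analysed set, the cost is lost precision in an exploratory comparison. Under the assumed SD of 0.5 to 0.6 log10 and share of 30% to 50%, adding the term narrows the interval by at most about 2.5-4% at 2-fold, 6-10% at 3-fold and 9-14% at 4-fold. With one formulation, or a small difference between formulations, the loss is nil or negligible. The omission does not make the arm comparison invalid, and the primary analysis is not touched.

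**What to change.** Add COVID-19 vaccine formulation at Visit 1 (original-strain or variant-containing) to the EO8 ID50/ID80 regression as a pre-specified fixed effect next to platform and site. State that the term is dropped if only one formulation was used. Allocation decides only the order of IIV4 and placebo, so formulation should not depend on group and can be treated as a baseline factor. Report the Simultaneous-to-Sequential ratio of geometric means by formulation in a descriptive table, without a test.

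Derive formulation from the recorded product and lot data, and check vaccination records for doses given as standard of care. The cost is one model term, one table and that record check. No new samples or participant contacts are needed.
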